4.7.1.3 Reporting of serious adverse events

Investigators and other site personnel must inform appropriate AstraZeneca representatives of any SAE that occurs in the course of the study within 1 day (i.e., immediately but no later than the end of the next business day) of when he or she becomes aware of it.

The AstraZeneca representative will work with the investigator to compile all the necessary information and ensure that the appropriate AstraZeneca Drug Safety Department receives a report by day one for all fatal and life-threatening cases and by day five for all other SAEs.

Follow-up information on SAEs must also be reported to AstraZeneca by the investigator within the same time frames.

If a non-serious AE becomes serious, this and other relevant follow-up information must also be provided to AstraZeneca within 1 day as described above. For a non-serious AE that becomes serious but which is not fatal or life-threatening a report should be received within 5 days.

All SAEs have to be reported, whether or not considered causally related to the investigational product or to the study procedure(s). All SAEs will be recorded in the case report form. The investigator is responsible for informing the Ethics Committee and/or the Regulatory Authority of the SAE as per local requirements.

The adverse event dictionary used at the beginning of this study will be MedDRA v 5.1. Any new versions released will be implemented as appropriate.

4.7.2 Laboratory safety measurements and variables

4.7.2.1 Methods of assessment

During the conduct of this study, a central laboratory (Quintiles Laboratories) will be utilised for the analysis of haematology and biochemistry values in order to assure standardisation of assessments and meaningful comparisons between the two treatment arms. However, the local laboratory in each centre may be used to perform any laboratory assessments required by the investigator as part of the routine medical management of the patient.

For the purpose of assessing eligibility, patients may be screened within 3 weeks prior to randomisation by a local laboratory. However, all patients must have a baseline haematology and biochemistry evaluation performed by the central laboratory within 7 days prior to treatment. For participating centres, the central laboratory will be performing all laboratory safety measurements for this study. For centres in countries where use of the main study central laboratory is not possible, a local Central Laboratory may be used if available, if not, a centre-specific local laboratory may be used.

The central laboratory may be used to determine eligibility if performed in time to allow review of the results within 7 days before randomisation and treatment. Results from the local laboratory may be used to determine eligibility should the investigator wish to treat the patient prior to the receipt of the results from the central laboratory. Further samples will be assessed at the timepoints detailed in the study plan (see [Table 1](#)).

The central laboratory will supply all venepuncture equipment, sample containers and labels. Procedures for sampling, handling and shipping of these samples will be provided in the Laboratory Handbook for Investigators to be provided to each site.

The following laboratory parameters will be investigated. See Section [4.8](#) for the total volume of blood samples to be collected.

Table 4 Biochemistry (serum gel tube)

Alanine aminotransferase (ALT)	Creatinine
Aspartate aminotransaminase (AST)	Total bilirubin
Alkaline phosphatase (ALP)	

Table 5 Haematology (ethylene diamine tetra-acetic acid [EDTA] coated tube)

White blood cell count (total)	Absolute Neutrophil Count (ANC)
Haemoglobin	Platelet count

4.7.2.2 Derivation or calculation of outcome variables

Section 4.7.1.2 (x) provides details of how AEs based on laboratory tests will be recorded and reported.

4.7.3 Vital signs, ECG and physical examination

4.7.3.1 Methods of assessment

Vital signs (heart rate and blood pressure) and physical exam are performed at each dosing visit with the exception of visit 2.

ECG is only recorded routinely at screening and in the event of a cardiac adverse event. The same method of assessment should be used throughout. ECG will be evaluated locally and the results recorded on the relevant CRF page. Any clinically significant abnormal findings observed and recorded during the study will be recorded as AEs.

Physical examinations will be performed and will also include the WHO performance status.

WHO performance status will be recorded as follows:

- 0 = Fully active, able to carry out all usual activities without restrictions and without the aid of analgesia
- 1 = Restricted in strenuous activity, but ambulatory and able to carry out light work or pursue a sedentary occupation. This group also contains patients who are fully active, as in Grade 0, but only with the aid of analgesics
- 2 = Ambulatory and capable of all self-care, but unable to work. Up and about more than 50% of waking hours
- 3 = Capable of only limited self-care, confined to bed or chair more than 50% of waking hours
- 4 = Completely disabled, unable to carry out any self-care and confined totally to bed or chair.

4.7.3.2 Derivation or calculation of outcome variables

Any new medical condition reported during the study will be recorded as an AE. Only those findings that are in addition to the condition being treated will be recorded as AEs (see

Section 4.7.1.2 for recording of AEs). Conditions that are considered by the investigator to be unequivocally disease-related will not be recorded as AEs.

4.8 Volume of blood sampling and handling of biological samples

The total volume of blood drawn from each patient will depend on the length of time the patient receives study medication. Table 6 is a guide to the approximate volume of blood that will be drawn from each patient, based on the assumption that each patient will receive study treatment for 24 weeks.

Table 6 Volume of blood to be drawn from each patient

Assessment		Sample volume (ml)	No. of samples	Total volume (ml)
Safety	Biochemistry	3.5	5	17.5
	Haematology	2	5	10
Total				27.5

During the survival follow up phase, no further central laboratory blood samples will be taken for this protocol.

4.8.1 Analysis of biological samples

4.8.1.1 Biochemistry samples

The analyte stability limits defined by Quintiles Laboratories will be applied to all analyses performed on behalf of AstraZeneca. Quintiles Laboratories will not analyse samples that fall outside these stability limits. Analytical data will not be reported if found to have been derived from a sample that fell outside these stability limits. The standards of procedure followed by Quintiles Laboratories may be amended in accordance with its Standard Operating Procedures. Quintiles Laboratories will inform AstraZeneca (or company representing AstraZeneca) of the stability limits relevant to this study before the first patient gives informed consent to take part in the study.

If Quintiles Laboratories chooses to sub-contract the analytical work to another laboratory, Quintiles Laboratories must assure itself and provide assurance to AstraZeneca (or company representing AstraZeneca) that the other laboratory will apply defined stability limits to all analyses performed on behalf of AstraZeneca. Samples falling outside these limits must not be analysed or data reported. The other laboratory will inform AstraZeneca (or company representing AstraZeneca) of the stability limits relevant to this study before the first patient gives informed consent to take part in the study.

4.9 Genetic measurements and co-variables

For those centres considering the collection of blood samples for genetic analysis: Patients will be invited to contribute a single 9 ml blood sample for extraction of DNA for potential genetic analysis. Patients' participation in this genetic component is voluntary and any patient's decision not to participate will not exclude them from the main clinical study.

Further details regarding blood sample collection, storage, extraction of DNA and analysis are available in Appendix F.

4.10 Collection of tissue samples

A tumour block (paraffin-embedded tumour tissue) from either the primary tumour or a metastatic site (in the latter case the sample will have been obtained before that the study drug has been started) will be sent to the coordinating centre for each patient participating in the tumour tissue study, provided that the patient has given her written informed consent.

All tumour samples from a given participating centre will be submitted to the coordinating centre after which the translational research study accrual will be closed.

Available samples will have to be sent by courier to the following address :

Faslodex translational research study c/o

Upon receipt of the tumour block, appropriate data will be recorded in the translational research study data-base and, immediately after, the sample will be processed in order to extract a core biopsy that will be incorporated in a tissue micro-array (TMA). After the completion of this operation the tumour block will be immediately returned to the participating centre.

It is foreseen that the time elapsing from the date of the tumour block receipt at the coordinating centre and the date the tumour block will be mailed back to the participating centre will be four weeks.

TMA sections will be sent from the coordinating centre to a central laboratory with large experience in the evaluation of those biological markers that will be investigated in the translational research study. If the patient will withdraw her consent to the translational research study, the corresponding sample will be removed from consideration for any future study use (see Section 3.3.5.3).

Biological data will be entered in the translational research study database. The latter will be located at the coordinating centre in (see address above) where data management and statistical analysis will also be performed.

For any additional information regarding this study please contact _____ at the address indicated above or at the following e-mail address :

5. DATA MANAGEMENT

Case Report Forms will be provided for the recording of data. The forms will be 4 level NCR (no carbon required) paper. Data is to be recorded legibly onto the case report forms in black or blue ballpoint ink. Corrections should be made legibly and initialled and dated by approved personnel; the reasons for significant changes must be provided. Correction fluid or covering labels must not be used. The top original, 1st and 2nd copy of each completed form will be collected. The top original and the 1st copy will be sent to data management personnel at the CRO, the 2nd copy will be retained by the monitor. The 3rd copy will be retained at the investigator site.

Any electronic data will be electronically loaded into the database by the CRO and checked for validity.

The method of distribution of data queries will be documented in the study Data Management Plan. The original signed data query will be returned to the CRO. The monitor will retain one copy and the other retained at the investigator site. On receipt of the data query by data management at the CRO the database will be edited appropriately.

5.1 Reporting of Translational Research Results

Results from any translational research performed will be reported separately from the clinical trial report. AstraZeneca and the translational research coordinating centre will not provide individual results to patients, their family members, any insurance company, an employer, clinical study investigator, general physician or any other third party, unless required to do so by law. The patient's tissue will not be used for any purpose other than those described in the study protocol.

Individual patients will not be identified in any report or publication resulting from this work. The data and results of this study may be reviewed with collaborators and published, but neither the patient's name nor any other personal identifiers will appear in any publication or report.

6. STATISTICAL METHODS AND DETERMINATION OF SAMPLE SIZE

6.1 Statistical evaluation – general aspects

A comprehensive Statistical Analysis Plan (SAP) will be prepared before un-blinding of the data, or in instances where the data are not blinded, database lock.

6.2 Description of outcome variables in relation to objectives and hypotheses

The primary objective of the study is to compare the efficacy of 500 mg fulvestrant with 250 mg fulvestrant. This will be assessed by the primary variable of time to progression, which is defined in Section 4.6.1.

A secondary objective of the study is to compare objective response rate, overall survival, clinical benefit rate, duration of clinical benefit and duration of response of 500 mg fulvestrant with 250 mg fulvestrant. The secondary variables ORR, OS, CBR, DoCB and DoR are defined in Section 4.6 and TOI in Section 4.3.

A further secondary objective of the study is to assess tolerability of fulvestrant 500 mg compared with fulvestrant 250 mg. Tolerability will be assessed by adverse events, which are defined in Section 4.7.1.1.

6.3 Description of analysis sets

The primary statistical analysis of the efficacy of 500 mg fulvestrant compared to 250 mg fulvestrant will include all randomised patients and will compare the treatment groups on the basis of randomised treatment, regardless of the treatment actually received. Therefore efficacy data will be summarised and analysed on an intention-to-treat (ITT) basis. This approach will be used when assessing time to progression, objective response rates, overall survival, clinical benefit rates, duration of clinical benefit and duration of response. Analyses on QoL data will be carried out using the ITT population as primary and will also be performed by study treatment actually received as supportive.

In addition, a per protocol (PP) analysis excluding significant protocol violators and deviators will be carried out for the primary variable of TTP using the model with treatment factor only.

A subgroup analysis based on ITT will be performed for patients who are both ER+ and PgR+ for the variables of TTP, ORR, OS and CBR.

When assessing tolerability of 500 mg fulvestrant against 250 mg fulvestrant summaries will be produced based on study treatment actually received.

6.4 Method of statistical analysis

The hypothesis being tested in this study is:

H₀: 500 mg fulvestrant is no different than 250 mg fulvestrant

H₁: 500 mg fulvestrant is different from 250 mg fulvestrant

The hypothesis testing for treatment differences will be performed for TTP, ORR, OS and CBR. The superiority of 500 mg fulvestrant will be declared if the two-sided p-value for the treatment comparison is ≤ 0.05

No formal analysis will be performed on DoR or DoCB.

The primary analysis on the primary variable of TTP will be performed using a log-rank test (equivalent to the Cox's proportional hazards regression model with treatment factor only) in ITT population.

In addition to the log rank test for TTP (unadjusted model with treatment factor only) a Cox's regression model will also be performed with factors fitted for treatment and other baseline covariates (adjusted model).

The conclusions will be based on the unadjusted log rank test analysis as this is considered as the primary analysis. If the unadjusted analysis and the adjusted analysis yield different results, the consequence of covariate adjustment will be explored.

A secondary Per Protocol analysis of TTP will be performed using a log-rank test in order to assess the reliability of the conclusions from the primary ITT analysis.

For objective response rate and clinical benefit rate, a logistic regression model will be fitted with treatment factor only. For overall survival the log rank test will be performed (as described above for TTP). Duration of response and duration of clinical benefit will be summarised using the Kaplan-Meier method.

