2.2 Secondary objectives

Secondary Objective	Variable
1. To compare the objective response rate of patients treated with fulvestrant 500 mg with the objective response rate of patients treated with fulvestrant 250 mg.	Objective Response Rate (ORR = CR + PR defined by RECIST criteria)
2. To compare clinical benefit rate of patients treated with fulvestrant 500 mg with the clinical benefit rate of patients treated with fulvestrant 250 mg.	Clinical Benefit Rate (CBR = CR + PR + SD \geq 24weeks defined by RECIST criteria)
3. To compare duration of response of patients treated with fulvestrant 500 mg with the duration of response of patients treated with fulvestrant 250 mg.	Duration of Response (DoR)
4. To compare the duration of clinical benefit of patients treated with fulvestrant 500 mg with the duration of clinical benefit of patients treated with fulvestrant 250 mg.	Duration of Clinical Benefit (DoCB)
5. To compare the overall survival of patients treated with fulvestrant 500 mg with the overall survival of patients treated with fulvestrant 250 mg.	Overall Survival (OS)
6. To assess the tolerability of fulvestrant 500 mg treatment compared with fulvestrant 250 mg treatment.	Frequency and Severity of Adverse Events

THIS IS A PRINTED COPY OF AN ELECTRONIC DOCUMENT. PLEASE CHECK ITS VALIDITY BEFORE USE.

Secondary Objective	Variable
7. To assess the quality of life (QoL) of patients treated with fulvestrant 500mg as compared to fulvestrant 250 mg in a subgroup of patients.	Trial outcome index (TOI) derived from the FACT-B questionnaire. Data will be collected from a subgroup of patients.

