4.6.5 Duration of Clinical Benefit (DoCB)

4.6.5.1 Method of assessment

Duration of clinical benefit will be calculated for those patients with a best response of CR, PR or SD \geq 24 weeks.

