4.6.6 Duration of Response (DoR)

4.6.6.1 Methods of assessment

DoR will be calculated for those patients who have a best response of CR and PR based on RECIST criteria (Appendix C).

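### Objectives 3 and 4 promise a comparison of DoR and DoCB between doses, but the plan gives only per-arm medians in patients selected by outcome

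*Protocol*

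**What the plan says.** Section 2.2 of the protocol words both objectives as comparisons. Objective 3 is "To compare duration of response of patients treated with fulvestrant 500 mg with the duration of response of patients treated with fulvestrant 250 mg". Objective 4 is "To compare the duration of clinical benefit of patients treated with fulvestrant 500 mg with the duration of clinical benefit of patients treated with" the 250 mg dose. Section 6.2 repeats this: "A secondary objective of the study is to compare objective response rate, overall survival, clinical benefit rate, duration of clinical benefit and duration of response".

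Section 6.4 restricts inference: "The hypothesis testing for treatment differences will be performed for TTP, ORR, OS and CBR". For the two durations it says "No formal analysis will be performed on DoR or DoCB". Section 6.4.4 then provides Kaplan-Meier plots and medians for each randomised arm. It gives no hazard ratio, difference or interval between arms.

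The patients who contribute are defined by outcome. Section 4.6.6.1: "DoR will be calculated for those patients who have a best response of CR and PR" (that is, either category). Section 4.6.5.1: "Duration of clinical benefit will be calculated for those patients with a best response of CR, PR or SD" lasting at least 24 weeks. Section 4.6.6.2 gives DoR two start dates, first documented response and randomisation, but keeps the same subset for both.

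Section 6.3 describes the intention-to-treat approach as including all randomised patients by randomised arm. The list of variables it covers ends with "overall survival, clinical benefit rates, duration of clinical benefit and duration of response".

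**The concern.** Randomisation makes the arms comparable as a whole. It does not make responders on 500 mg comparable with responders on 250 mg, because the dose may influence who becomes a responder. Suppose 500 mg turns some patients who would not have responded into responders of shorter duration. Those patients gain, yet they pull down the median among responders on 500 mg. The per-arm medians could then favour 250 mg even though no patient does worse on 500 mg.

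The protocol's own rationale makes a shift in subset membership plausible. Section 3.2.1 hopes that reaching steady state sooner will avoid early progressions, which would move some patients into the response or benefit subset on 500 mg only.

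At stake is the answer to two of the seven secondary objectives. The per-arm medians are the only planned output on duration, and nothing in the protocol warns that they are not a randomised comparison.

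**Working it through.** **1. Objectives against planned output**

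| | Stated aim (2.2, 6.2) | Patients included | Planned output (6.4, 6.4.4) |
|---|---|---|---|
| DoR | compare doses | CR or PR | KM plot and median per arm |
| DoCB | compare doses | CR, PR or SD ≥ 24 weeks | KM plot and median per arm |

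Neither row contains a between-arm estimate.

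**2. The plan's own figures.** The protocol gives no design figure for DoR or DoCB. The nearest is in Section 6.5: median TTP of 5.5 months on 250 mg and hazard ratio 0.8, so 5.5 / 0.8 = 6.875 months, stated as 6.88. It is used in step 5.

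**3. DoR illustration**

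Inputs from Section 3.2 (earlier trials of fulvestrant): response rate 19.2%, median DoR 16.7 months.

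Assumptions, not in the protocol:
- durations are exponential;
- the rate applies to randomised patients with measurable disease;
- patients who would respond on 250 mg keep the same duration on 500 mg;
- 500 mg adds 3 to 10 percentage points of responders with median DoR of 6 to 12 months.

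Expected time in response per randomised patient with measurable disease = response rate × mean duration, where mean = median / ln 2.

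- 250 mg: 0.192 × 16.7 / 0.693 = 4.63 months.
- 500 mg, middle case (+5 points, median 8 months): 4.63 + 0.05 × 8 / 0.693 = 5.20 months.

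The median among 500 mg responders solves w × 0.5^(t/16.7) + (1 − w) × 0.5^(t/8) = 0.5, with w = 0.192 / 0.242 = 0.793. This gives t = 14.2 months, against 16.7 on 250 mg.

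Over the 12 scenarios (+3, +5 or +10 points; median 6, 8, 10 or 12 months), the responder median on 500 mg is 11.5 to 15.9 months, against 16.7. Expected time in response is 4.89 to 6.36 months, against 4.63 (ratio 1.06 to 1.37). The two summaries disagree in all 12. That follows from assuming that every added responder lasts less long than the existing ones.

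If 500 mg also lengthens existing responders' durations by 10%, the responder median is still shorter on 500 mg in 9 of 12 scenarios.

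**4. DoCB illustration**

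Input from Section 3.2: clinical benefit rate 43.5%. Assumptions: residual median of 5.5 months after week 24 on 250 mg; 500 mg adds 5 to 10 points with residual median 1 to 3 months; exponential residuals. Week 24 is 24 × 7 / 30.4375 = 5.52 months.

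- 250 mg median: 5.52 + 5.5 = 11.0 months.
- 250 mg expected duration: 0.435 × (5.52 + 5.5 / 0.693) = 5.85 months.
- 500 mg median: 9.6 to 10.7 months.
- 500 mg expected duration: 6.20 to 6.84 months.

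**5. A case with no reversal**

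Take TTP as exponential in both arms with hazard ratio 0.8, and benefit as being progression-free at 24 weeks. Median DoCB is then 5.52 + 5.5 = 11.0 months on 250 mg and 5.52 + 6.875 = 12.4 months on 500 mg. The subset medians point the right way.

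**The case against.** The strongest reply is that the plan already takes the cautious course. Declining to test a subset selected by outcome is sound, and a descriptive side-by-side display remains. This stands. A reader might infer that the plan should have tested DoR and DoCB in these subsets, or that nothing at all will be shown on objectives 3 and 4. The documents support neither. What is missing is an estimate of the promised comparison that randomisation protects.

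A second reply is that randomised comparisons of the related quantities exist. ORR and CBR are tested. DoCB also runs from randomisation to progression or death (Section 4.6.5.2), the same start and event as TTP (Section 4.6.1.2), and TTP is compared in all randomised patients. This limits the consequences considerably. It does not supply a comparison of duration: TTP includes bone-only patients, whom Section 4.6 keeps out of the duration summaries, and TTP does not measure time in response.

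A third concerns Section 6.3. A reader might infer that it flatly contradicts Sections 4.6.5 and 4.6.6. It need not. ORR and CBR stand in the same list although they too are limited to measurable disease, and Section 6.4.4 speaks of randomised treatment. The workable reading is grouping by randomised arm, so the wording is loose rather than a conflicting rule.

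Finally, the illustration depends on assumed short-lived added responders and on exponential durations. Treating 16.7 months as a mean rather than a median would put the 250 mg figure at 0.192 × 16.7 = 3.21 instead of 4.63 months. The level is therefore soft; the opposite direction of the two summaries is the point being illustrated.

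**Conclusion.** The point holds in a limited form. Objectives 3 and 4 and Section 6.2 state a comparison of DoR and DoCB, and no planned estimate delivers it with the protection of randomisation. A later SAP could add detail, but the exclusion of formal analysis is fixed in the protocol itself.

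The per-arm medians could point the opposite way to the effect over all patients. In the assumed middle case the responder median is 14.2 against 16.7 months, while expected time in response is 5.20 against 4.63 months per randomised patient with measurable disease. This rests on added responders with shorter durations, a figure the protocol does not give. A reader might infer that a reversal is likely; the documents do not show that, and under simple exponential TTP at the design hazard ratio it does not occur for DoCB.

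The primary analysis and the tested variables (TTP, ORR, CBR, OS) are unaffected. The remedy is a cheap improvement to two secondary objectives.

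**What to change.** - Add a supportive between-arm estimate of expected duration of response and of clinical benefit, by randomised arm, in all randomised patients with measurable disease at baseline. Count zero for patients without response or benefit. Report a ratio or difference with a 95% CI, and state the truncation time or parametric model used to handle censoring.
- Label it post hoc if it is added now, since Section 3.1 says the primary TTP analysis and the 50% survival analysis were performed together and describes what follows them.
- Keep the Kaplan-Meier curves in the outcome-defined subsets as descriptive, with a caveat that they are not protected by randomisation.
- Clarify in Section 6.3 that for the subset summaries of DoR and DoCB, intention to treat means grouping by randomised arm within those subsets.

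The cost is some analysis wording and one derived table from data already collected. The added estimate depends on the chosen truncation time or model, so that choice must be stated. It will also rest on few responders: with 360 patients per arm and a 19.2% response rate, 360 × 0.192 = 69 per arm if all had measurable disease, or 35 if half did (the share is not given in the protocol).
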